## Please note the following information:

The Board requires that all adult participants must be able to consent for themselves to be enrolled in this study. This means that you cannot enroll incapable adult participants who require enrollment by consent of a legally authorized representative.

## 1. Study Overview

### 1.1 Background and rationale

Late-onset Alzheimer's disease (LOAD) develops over a long preclinical period during which cognitively normal (CN) individuals accumulate Alzheimer's pathology and subtle cognitive changes before reaching mild cognitive impairment (MCI) and dementia. Plasma and CSF pTau217 have emerged as highly accurate biomarkers for Alzheimer's pathology and for predicting conversion from MCI to Alzheimer's dementia, with reported AUCs in the 0.8–0.9 range for progression and for detection of underlying pathology. Clinical Dementia Rating Sum of Boxes (CDR-SB) has been extensively validated for staging from normal cognition through very mild impairment and MCI, and small changes in CDR-SB (0.5–1 point) correspond to clinically meaningful transitions. However, this neurocognitive assessment needs an informant to be present with the patient and is not part of the standard primary care process for evaluating individuals who are cognitively normal. Our study will utilize an Oura Ring Data Risk Assessment, a self-administered Digital Cognitive Assessment, Speech Biomarker Assessment, Lifestyle History Questionnaires, and EMR risk assessments scoring for the initial screening of Cognitively Normal Subjects for any evidence of existing Cognitive Impairment and Assess their expected Risk of Progressing to SCD/MCI after the inclusion of proteogenomic risk scores..

We are currently performing Insilco work to validate proteogenomic progression and risk (P&R) models.) The current data suggests that integration of An Ancestry and Sex normalized Polygenic Risk Score (PRS) with proteomic profiles can predict near-term conversion probability of CN subjects to AD-MCI with clinically useful AUC-ROC values. These Insilco models were developed in existing cohorts of CN and MCI participants with proteogenomic biomarker data, and will be used to select the best performing model that is able to integrate with EMR risk data (that includes lifestyle risk information and wearable data), into a multimodal (P&R) model that categorizes low, medium, and high risk of conversion to pTau217 positive MCI from Cognitively Normal Individuals with specific risk factors. It is also designed to

categorize SCD subjects with low, medium, and elevated risk of conversion probability to pTau217 positive MCI). The model and pilot data will be used to estimate annual conversion rates from CN to AD-MCI, which will in turn inform sample size and follow-up duration of the 2 year proof of concept studies

## **Polygenic risk scores (PRS) in Alzheimer's disease**

Late-onset Alzheimer's disease (AD) is highly polygenic, with common variants of small effect across the genome contributing to risk in addition to APOE  $\epsilon$ 4. Polygenic risk scores (PRS) aggregate the weighted effects of large numbers of AD-associated single nucleotide polymorphisms (SNPs), typically using effect sizes from genome-wide association studies (GWAS), to generate an individual-level measure of inherited susceptibility. In AD, such scores, especially when combined with APOE, can identify individuals at markedly elevated odds of developing disease and earlier age at onset compared to those in the lowest PRS strata.

Several large GWAS and meta-analyses have now demonstrated that AD PRS discriminate cases from controls with AUC values commonly in the 0.70–0.80 range, and that individuals in the highest PRS percentiles can have more than a ten-fold higher odds of AD compared to those in the lowest percentiles when stratified by APOE genotype. PRS performance has been replicated across independent European and non-European cohorts and shows a stepwise relationship with incident AD dementia, age at symptom onset, and amyloid deposition. These data support the feasibility of using PRS, in conjunction with APOE and biomarker measures, for risk stratification and enrichment of preclinical and prodromal AD cohorts.

In addition to traditional GWAS-based scores, recent work has explored integrative or “multi-domain” polygenic scores that combine loci implicated in neurodegenerative and vascular pathways, as well as deep-learning–based approaches to optimize SNP weighting and capture non-linear effects. Such integrative scores can improve prediction of dementia onset and may better reflect the heterogeneous biology of AD, including vascular and metabolic components. Together, this literature motivates the use of a validated, APOE-aware PRS as one input into a broader proteogenomic risk (PR) model to stage cognitively normal (CN) individuals along a preclinical AD continuum in this study.

This protocol describes a FIH 2-year observational study to evaluate the Incident Prediction & Risk model's ability to predict conversion among ApoE4-positive adults,

with intensive plasma proteomic, genomic risk assessment, , neurocognitive assessments, and wearable device data. I,

## 1.2 Objectives and specific aims

This first-in-human observational study is primarily designed as a pilot feasibility and prospective validation of a pre-specified proteogenomic Progression and Risk (P&R) model for predicting conversion from cognitively normal (CN) or very mildly impaired status to pTau217-positive mild cognitive impairment (MCI) in ApoE4-positive older adults. Secondary and exploratory aims evaluate additional omic and digital measures, as well as the practical scalability and cost of the assessment protocol.

### Primary aims

1. Validate the fixed P&R model's ability to discriminate participants who convert to pTau217-positive MCI Stage I within 24 months from those who remain non-converted, among ApoE4-positive adults aged  $\geq 55$  years.
2. Assess the feasibility and acceptability of the multimodal assessment protocol over 24 months, including recruitment of ApoE4-positive individuals with existing genomic data, completion of scheduled visits and biospecimen collections, and adherence to Oura Ring and digital cognitive assessments.

### Secondary aims

3. Compare the prognostic performance of the P&R model with simpler baseline models (e.g., APOE + PRS only, or clinical + cognitive only) for predicting CN  $\rightarrow$  pTau217-positive MCI conversion over 24 months.
4. Estimate, with appropriate uncertainty, short-term (2–5-year) conversion probabilities derived from the P&R model and explore how these inform projected longer-term (up to ten-year) risk in this population, recognizing that extrapolations will be preliminary and supported by external cohorts.
5. Evaluate the practical scalability and relative cost of alternative sampling and visit strategies, including venous versus capillary (fingerstick) blood collection and varying degrees of in-clinic versus remote assessment, using simple per-participant and per-conversion cost summaries.
6. Assess the incremental predictive value, beyond the core P&R model, of selected digital and wearable measures (e.g., Oura-derived sleep and activity metrics, brief speech, and digital cognitive features) for detecting CN  $\rightarrow$  MCI conversion events.

7. Determine the relationship between an Oura Ring–based exposome risk score and proteogenomic risk scores and cognitive-functional measures.

## Exploratory aims

8. Evaluate the performance of the P&R model within subsets of CN participants at higher predicted near-term risk (e.g., upper P&R risk strata) to explore whether focusing on such high-risk groups could improve time-to-signal and statistical power for future larger studies.
  9. In a subset of participants and as data and budget permit, explore how combinations of plasma pTau217, other plasma markers, and optional measures (such as amyloid PET, retinal hyperspectral imaging, and provoked EEG, when available from clinical care) refine staging and prediction beyond the core P&R model.
- 

## 2. Study Design

### 2.1 Overall design

Longitudinal retro and prospective , observational cohort study of up to 90 ApoE4-positive adults (age  $\geq 55$ ) followed for 24 months, with in-person visits every 6 months and continuous remote monitoring with Oura Ring and a subset of 10 subjects. No investigational drug or device is administered. Participants will undergo venous or capillary blood collection, CSF collection as part of this study are not performed, digital cognitive and speech biomarker assessments,( EEG, retinal imaging or MRIs may be performed outside of this study if ordered by referrals and shared by agreement with this study. Particularly in subjects that convert during this study.

Samples and data will be used to (a) apply and refine the Insilco-derived P&R model for conversion prediction, and (b) compare model-predicted risk with the study observed conversion events.

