## Practical use

- Fit a multivariable Cox model with one or more of the following predictors-X.
  - Polygenic Risk score - stratified to 5 ApoE Genotyped Categories
  - EMR-Lifestyle Risk Score = Dementia Risk Score
  - Proteomic Risk Score - stratified to 5 ApoE Genotype Categories
  - mDNA Risk score
  - Proteome Structure Based Risk Score
  - circRNA based Risk Score
  - MRI based Risk Score
  - PET Scan based Risk Score
  - EEG based Risk Score
  - Neurocognitive based Risk Score
  - Metabolome based Risk Score
- Use the estimated coefficients (or per-unit HRs) to compute the linear predictor for each subject.
- Exponentiate that linear predictor to get a single combined hazard ratio relative to a chosen reference profile; this can then be scaled or categorized as a “risk score.” or some may call an Aging Score.

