### **4.3 Follow-up visits (Months 6, 12, 18, 24)**

At each follow-up:

- Interval history, adverse events, and medication changes.
- CDR (global and CDR-SB) and a selected neuropsychological battery to detect MCI criteria and progression.
- Repeat digital cognitive assessments (Punto Health).
- Blood collection (venous and/or fingerstick) for plasma pTau217 and other biomarkers, plus proteomic/methylome panels as budget permits.
- Update on digital monitoring adherence and troubleshooting of devices.
- EEG and retinal imaging at selected visits (e.g., baseline and Month 24 for all, optional intermediate visits in a subset depending on resources).
- Additional imaging (MRI or amyloid PET) only when clinically indicated or available as standard-of-care.

Trigger-based assessments:

- If continuous monitoring or participant self-report suggests cognitive decline (e.g., sustained changes in speech patterns, activity, or sleep; decline in digital cognitive tasks), a targeted evaluation will be scheduled, including repeat CDR, brief neuropsychological testing, and biomarker sampling when feasible.

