### **4.4 Biospecimen handling and storage.**

Informed consent	X						
Inclusion / exclusion criteria	X	X	X	X	X	X	X
Medical / neurological / psychiatric history	X						
Medication review	X	X	X	X	X	X	X
Physical and neurologic examination		X				X	O
Vital signs (clinic or wearable)	X	X	X	X	X	X	X
Documentation of prior ApoE genotype and WGS / array data	X						
PRS calculation & stratification (once data available)		X					

CDR (global and CDR-SB, no-informant version)		X	X	X	X	X	X
Digital cognitive battery and brief speech measures (Punto Health)		X	X	X	X	X	O
BIOFLUID COLLECTION (core)							
Venous or capillary blood (pTau217 + core panel for P&R model)		X	X	X	X	X	X
Additional plasma markers (extended AD panel, as budget permits)		O	O	O	O	O	O
Blood methylome / other discovery omics (sub-cohort only)		O	O	O	O	O	O

Clinical labs from EMR or PCP (CBC, CMP, etc.)	0	0	0	0	0	0	0
CSF collection (clinically indicated lumbar puncture only)		0					0
Resting / provoked EEG (sub-cohort, if available clinically)		0				0	0
Retinal hyperspectral imaging (if available clinically)		0				0	0
Amyloid PET (standard-of-care only, if ordered by clinician)		0	0	0	0	0	0
MRI / structural imaging (standard-of-care only)		0	0	0	0	0	0

Digital devices and monitoring							
Oura Ring data linkage / device confirmation	O	X					
Continuous Oura monitoring (sleep, activity, HR metrics)		X	X	X	X	X	X
Digital monitoring adherence check (Oura + cognitive app)		X	X	X	X	X	X
Risk score calculation and staging							
Calculate P&R risk score and risk level		X	X	X	X	X	X
Update CN / SCD / MCI Stage I status and event determination		X	X	X	X	X	X

† Triggered visits or remote assessments will occur when digital monitoring, participant report, or clinical assessment suggests possible cognitive decline or functional change; they may include focused cognitive testing and repeat blood sampling for key biomarkers (e.g., pTau217) and will prompt referral to a neurologist if criteria for MCI with positive biomarkers are met.

---

Notes:

- Total in-clinic visits: 5 required (Baseline + 4 follow-ups at 6, 12, 18, 24 months), plus optional triggered visits.
- Total biospecimen collections: 5 venipuncture/capillary sessions minimum (Baseline + 4 follow-ups), plus optional triggered samples

Duration of participation: 24 months from baseline with continuous remote monitoring

---

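### Aim 9 uses EEG, retinal imaging and PET for prediction, but these tests depend on clinical referral and in converters tend to fall at or after conversion, so diagnosis could be read as prediction

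*Protocol*

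**What the plan says.** **Source of the tests.** Protocol section 2.1 states that "EEG, retinal imaging or MRIs may be performed outside of this study if ordered by referrals and shared by agreement with this study", and continues: "Particularly in subjects that convert during this study". The schedule table printed under section 4.4 makes EEG and retinal imaging conditional on clinical availability, and PET and MRI standard-of-care only. Section 4.3 has "Additional imaging (MRI or amyloid PET) only when clinically indicated or available as standard-of-care".

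**What happens at conversion.** Section 4.1 sends participants whose blood biomarkers turn positive to a neurologist and discharges them from the study. Digital monitoring and the five planned blood collections likewise run only for as long as the participant has not converted.

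**Use of the tests.** Aim 9 (section 1.2, exploratory aims) asks how "optional measures (such as amyloid PET, retinal hyperspectral imaging, and provoked EEG, when available from clinical care) refine staging and prediction", over and above what the P&R model gives. Section 5.2 lists EEG among the features whose incremental predictive value is assessed by AUC-ROC and net reclassification improvement. The predictor list under Practical use includes MRI and EEG scores and a "PET Scan based Risk Score" as possible terms in a Cox model.

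**Text pointing the other way.** Section 4.2 lists EEG among the baseline assessments with no clinical condition attached. Section 4.3 gives baseline and Month 24, for all participants, as the example timing for EEG and retinal imaging.

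**The concern.** A predictor has to be known before the event it predicts. Under section 2.1 and the schedule table, whether a participant has one of these tests depends on clinical referral, and section 2.1 expects this mostly in converters. The referral path in section 4.1 starts when biomarkers turn positive, which is part of the conversion definition in section 5.1. A test reached by that path describes a state that has already been entered.

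Two things are at stake. First, a measure that only reflects established MCI could be reported as improving prediction, and so be recommended for later, larger studies. Second, the tested subset would hold too many converters, so absolute risks and calibration computed in it would not apply to the cohort.

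**Working it through.** The protocol gives no conversion rate, no expected availability of these tests and no expected AUC for them, so there is no stated figure to reproduce. All inputs below are assumptions, chosen to show direction and range.

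**1. Test taken after conversion.** Suppose a marker is identically distributed in future converters and non-converters, and shifts by d standard deviations once conversion has occurred. If all converters are tested afterwards, AUC = Φ(d/√2).

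- d = 0.5: Φ(0.354) = 0.64
- d = 1.0: Φ(0.707) = 0.76
- d = 1.5: Φ(1.061) = 0.86

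If only a fraction f of converters is tested afterwards, AUC = 0.76f + 0.50(1 − f) at d = 1. With f = 0.5 this is 0.63. The true predictive AUC is 0.50 throughout.

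**2. Share of converters in the tested subset.** With conversion rate r and availability a1 in converters and a0 in non-converters, the share is r·a1 / [r·a1 + (1 − r)·a0].

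| True rate r | a1/a0 = 50/50% | 80/20% | 90/10% |
|---|---|---|---|
| 5% | 5% | 0.040/0.230 = 17% | 0.045/0.140 = 32% |
| 10% | 10% | 0.080/0.260 = 31% | 0.090/0.180 = 50% |
| 20% | 20% | 0.160/0.320 = 50% | 0.180/0.260 = 69% |

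Absolute risk in the tested subset is inflated whenever availability differs by outcome, even if every test is informative and well timed.

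**3. Does selective availability alone create a false AUC?** This was simulated with 400,000 subjects per scenario, using the rates and availabilities in the table, a core score with AUC about 0.75, and a marker unrelated to outcome. Among participants with the test, the marker's AUC was 0.497 to 0.503, and core plus marker equalled core alone. In 4,000 simulated studies of 90 participants (the size in section 2.1) at 80/20% availability, the marker was falsely significant at the 5% level in 4.5% of usable studies at a 10% conversion rate and in 4.8% at 20%. So it does not.

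**4. Do the conflicting passages remove the problem?** If EEG and retinal imaging are done at baseline in everyone, the baseline values precede conversion and do not depend on it, and the problem largely disappears for those values. A Month 24 value does not help. It lies at the end of the 24-month horizon, and participants discharged at conversion would not have one. MRI and PET are not covered by that text.

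**The case against.** A reader might infer that these measures will look predictive even if useless, simply because converters are tested more often. Step 3 shows otherwise. A spurious gain needs a further step: testing at or after conversion, having the test entered as a predictor, or imputation that encodes it. With an availability indicator in the model, the simulated core AUC of about 0.75 rises to about 0.88 at 80/20% availability, but the protocol plans no such model. Section 6.1 names multiple imputation only as an example, to be chosen by the mechanism of missingness.

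A reader might also apply the converter sentence to PET. That sentence names EEG, retinal imaging and MRI. PET is clinically ordered under other sections, but nowhere said to be concentrated in converters, and prior imaging is reviewed at screening.

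The list under Practical use is a menu of possible predictors, not a commitment. The P&R model components in section 2.2 include no MRI, PET or EEG, and the model is locked and scored at baseline, so the primary validation is untouched. Aim 9 explores rather than tests, and only "In a subset of participants and as data and budget permit, explore how combinations of plasma pTau217" and the other measures. It also covers staging, for which tests in converters are legitimate.

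All of this stands and limits the consequence. It does not remove the defect, because the protocol gives the tests a source linked to the outcome and a use that requires them to precede it. An analysis plan could add a timing rule, but could apply it only if the date and reason of each test had been recorded.

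**Conclusion.** The point holds in a limited form. Under section 2.1, section 4.1 and the schedule table, the availability of EEG, retinal imaging and MRI depends on conversion, and their timing probably does too. PET is clinically driven. Aim 9, and EEG in section 5.2, would then be unable to separate prediction from diagnosis.

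The size cannot be taken from the documents. Under the assumed post-conversion shifts of 0.5 to 1.5 SD, a marker with no predictive value would show an AUC of 0.64 to 0.86. At 80/20% availability, conversion rates of 5%, 10% and 20% would appear as 17%, 31% and 50% in the tested subset. That tests in converters fall mainly after the event is an inference from the referral and discharge path, not something the protocol states. For EEG and retinal imaging the conclusion also depends on which of the conflicting passages governs.

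**What to change.** - Restrict the prediction part of aim 9, and any AUC, net reclassification or Cox use of EEG, retinal, MRI or PET measures, to tests done before conversion and not prompted by a trigger, referral or suspected decline. Baseline measures are the cleanest, but other pre-conversion tests whose timing was not driven by decline can stay.
- Use tests done at or after a trigger, referral or conversion only to describe the staging of converters, and do not impute them for others.
- Record the date and the reason for each shared test.
- Reconcile section 2.1 and the schedule table (clinical availability only) with section 4.2 (EEG at baseline) and section 4.3 (EEG and retinal imaging at baseline and Month 24 for all).

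The cost is protocol wording and two recorded items per shared test. The drawback is that fewer participants contribute to an exploratory analysis, possibly too few to run it.

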## Definition and components of the PRS

The AD polygenic risk score used in this protocol will be derived from genome-wide SNP data using effect sizes from large, externally validated AD GWAS and meta-analyses, excluding the APOE locus so that APOE genotype can be modeled separately. Briefly, after standard quality control and ancestry checks, we will compute a PRS as the sum across selected SNPs of the number of risk alleles carried by the individual (0, 1, or 2) multiplied by the corresponding log-odds ratio for AD from the discovery GWAS. SNP selection and clumping will follow published best practices (e.g., linkage disequilibrium pruning and p-value thresholding) to balance predictive performance and parsimony.

The components of the PRS therefore include:

- Common autosomal SNPs associated with AD risk in prior GWAS, weighted by their reported effect sizes.
- Explicit separation of APOE  $\epsilon 2/\epsilon 3/\epsilon 4$  genotype, which will be modeled as an independent covariate (e.g.,  $\epsilon 4$  dose), consistent with evidence that optimal AD risk prediction treats APOE separately from the polygenic background.
- Optional incorporation of loci from integrative dementia scores (e.g., vascular, and neurodegenerative pathways) if they improve prediction in the pre-FIH Insilco phase; any such additions will be documented in the statistical analysis plan.

The raw PRS will be standardized (z-score) within an ancestry-matched reference population (e.g., external dataset plus early enrollees) and then categorized based on prespecified quantiles (e.g., lowest ~25%, next lowest 25%, next highest 25%, and highest ~25%), following prior work stratifying AD risk by PRS percentiles. These categories will be used for recruitment targeting (approximate balance of low, average, and high PRS) and for prespecified subgroup analyses of conversion risk.

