- Define 4 Categories CN individuals whose predicted 2–5-year conversion risk to MCI lies above a prespecified percentile cut-off (25 % lowest risk quartile, 25% next to lowest risk quartile, 25% next to highest risk quartile, and 25% highest risk quartile)
- Define 4 Categories of SCD whose predicted 2–5-year conversion risk to MCI lies above a prespecified percentile cut-off (25 % lowest risk quartile, 25% next to lowest risk quartile, 25% next to highest risk quartile, and 25% highest risk quartile)
- Estimate annual conversion rates within these model-defined groups (CN vs SCD), which are expected to differ by several-fold based on prior work showing strong stratification by proteomic, cognitive assessment, and multi-omic risk scores.

These estimated event rates (number of pTau217 positive MCI conversions per patient-years) are then used to justify the future FIH longitudinal sample size and follow-up duration described in Sections 1.2 and 3.2.

Fixed model for the FIH cohort

Once selected, the P & R model will be locked (fixed coefficients and included markers) before analysis of the FIH cohort. For each enrolled participant, we will calculate the P & R risk score at baseline and use it to:

- Assign CN participants to 4 CN Risk Levels and 4 SCD Risk Levels (per the thresholds derived above).
  - Generate individual predicted hazards of conversion for comparison with observed events (primary and secondary analyses).  
The FIH study itself is thus a prospective validation of a pre-specified P & R model developed entirely from existing data.
- 

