## 6. Statistical Considerations

### 6.1 General approach

Data analyses will be primarily exploratory and hypothesis-generating given the FIH nature and modest sample size, but key performance metrics (e.g., AUC-ROC) will be estimated with confidence intervals. Observational protocol templates recommend prespecifying primary analyses and sensitivity analyses for observational cohorts.

Analyses:

- Compute AUC-ROC for the P&R model and alternative models for predicting conversion to pTau217-positive MCI Stage I within 24 months.
- Compare AUC-ROC across models (proteogenomic vs proteo-methylome-genomic) using DeLong's test or similar.
- Use Cox proportional hazards models to estimate hazard ratios for time to conversion as a function of baseline P&R risk, PRS, ApoE4 dose, and biomarker levels.
- Use logistic regression and time-dependent ROC analyses for binary conversion endpoints over fixed time horizons.
- Incorporate digital monitoring variables as covariates and evaluate incremental predictive performance.
- For cost-effectiveness, compare costs and detection yield of different biospecimen and monitoring strategies using simple decision-analytic models (incremental cost per correctly predicted conversion).

Missing data will be handled using appropriate methods (e.g., multiple imputations, mixed-effects models) depending on pattern and mechanism of missingness. Sensitivity analyses will evaluate robustness of results to missing data assumptions.

---

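### Section 2.1 lets the study data refine a model that primary aim 1 treats as fixed, and section 6.1 does not say which version yields the reported AUC

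*Protocol*

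**What the plan says.** **The fixed-model statements.** Primary aim 1 (section 1.2) is to "Validate the fixed P&R model's ability to discriminate participants who convert to pTau217-positive MCI Stage I within 24 months". Section 2.2 adds "Once selected, the P & R model will be locked (fixed coefficients and included markers) before analysis of the FIH cohort", and concludes: "The FIH study itself is thus a prospective validation of a pre-specified P & R model developed entirely from existing data". The same part of section 2.2 says that each enrolled participant's baseline score will supply the predicted hazards that are compared with observed events, and it labels this use as primary and secondary analyses.

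**The statement that does not fit.** Section 2.1 lists two uses of the study's samples and data: "a) apply and refine the Insilco-derived P&R model for conversion prediction, and (b) compare model-predicted risk with the study observed conversion events". It gives no order, no data split, no exploratory label, and no distinction between a locked and a refined version.

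**The PRS input.** The section on the definition and components of the PRS standardises the raw score "within an ancestry-matched reference population (e.g., external dataset plus early enrollees", given as an example.

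**The analysis section.** Section 6.1 computes an AUC for the P&R model and for alternatives. It does not say whether the P&R model there is the locked one or a refined one.

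**The concern.** A validation AUC means something because the score was settled before the outcomes it is tested on. If coefficients or markers are adjusted on the study's conversions and the adjusted score is then compared with those conversions, the AUC is biased upwards. The bias is largest when events are few relative to the number of quantities being estimated. At 90 to 100 participants over 24 months, few events are plausible. The choice between locked and refined score could then decide what primary aim 1 appears to show, and the protocol leaves that choice open.

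The PRS reference raises a smaller version of the same problem. If early participants help set the mean and SD, one input to the score is not settled from existing data alone, and the scale may move while enrolment proceeds.

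**Working it through.** There is no protocol figure to reproduce: no event rate, target AUC, power or sample-size derivation is given. The check is a comparison of the text, then an illustration on stated assumptions.

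**1. Text, side by side.**

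| Question | Primary aim 1 and section 2.2 | Section 2.1, PRS section, section 6.1 |
|---|---|---|
| Do study data change the model? | No: coefficients and markers are fixed | Yes: refinement is a listed use (2.1) |
| Source of the model | Existing data only | PRS scale may draw on early enrollees (PRS section) |
| Score used in the primary analysis | Locked baseline score (2.2) | Version not identified (6.1) |
| When is it locked? | Before analysis of the cohort (2.2) | Not addressed |

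On timing, model staging is already applied at eligibility (section 3.3) and at baseline (section 4.2). The lock therefore has to exist before the first participant is scored. Section 2.2 implies that order but does not state it.

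**2. What a refit would do to the AUC.**

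Inputs from the protocol: N = 90 (section 2.1) or 100 (section 3.2), and 24 months of follow-up. Five predictors is the size of the protocol's Cox formula; 11 is the number of scores listed under Practical use. Both serve only as example sizes.

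Assumed: conversion of 5%, 10% or 20%, giving 4, 9 or 18 events at N = 90 (4.5 rounded to 4) and 5, 10 or 20 at N = 100.

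Method: independent normal predictors, each shifted in converters by δ/√p, with δ = √2·Φ⁻¹(true AUC). A very lightly penalised Cox model was refitted in each of 300 simulated cohorts per setting. Ranges below are means across the six combinations of N and event rate.

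| True AUC | Locked score | Refit, same cohort, 5 predictors | Refit, same cohort, 11 predictors | Refitted model in new data (5 or 11) |
|---|---|---|---|---|
| 0.50 | 0.49–0.50 | 0.65–0.79 | 0.72–0.91 | 0.50 |
| 0.70 | 0.69–0.72 | 0.74–0.84 | 0.79–0.93 | 0.57–0.66 |
| 0.80 | 0.79–0.81 | 0.82–0.88 | 0.85–0.95 | 0.67–0.77 |

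Events per predictor run from 4/5 = 0.8 to 20/5 = 4.0 with five predictors, and from 4/11 = 0.4 to 20/11 = 1.8 with eleven. The locked score is essentially unbiased throughout. The refitted score looks better in the same cohort and performs worse than the locked score elsewhere whenever there is real signal.

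This is a full refit. A milder update that only rescales the linear predictor by a positive factor, or changes the baseline hazard, keeps the ranking and so leaves the AUC as it is.

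**3. Precision of the locked-score AUC.** The Hanley–McNeil standard error is √{[A(1−A) + (e−1)(q₁−A²) + (n₀−1)(q₂−A²)]/(e·n₀)}, with q₁ = A/(2−A) and q₂ = 2A²/(1+A). For A = 0.80, e = 10 and n₀ = 90: q₁ = 0.667, q₂ = 0.711, SE = √[(0.16 + 0.24 + 6.33)/900] = 0.086, half-width 1.96 × 0.086 ≈ 0.17. Over the six settings the half-width runs from 0.27 (4 events) to 0.12 (20 events). The locked result is honest but imprecise, and that makes a more flattering refined figure tempting.

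**4. The PRS reference.** A common shift in the PRS moves every score equally, so ranks and AUC do not change. Suppose the PRS is one of five equally informative inputs, coefficients are fixed, and its scale is multiplied by c. Then AUC = Φ{0.8416·(4+c)/√[5(4+c²)]} for a starting AUC of 0.80. At c = 1.4 this is Φ(0.8416 × 5.4/5.459) = Φ(0.8325) = 0.797; simulation gives 0.797. At c = 0.7, simulation gives 0.798. The effect on AUC is negligible. Absolute risk is a different matter: with coefficient β per SD, a shift of s SD multiplies every predicted hazard by exp(βs), and participants near a cut-off change category.

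**The case against.** The best defence is that the protocol is mostly clear. Aim 1 and section 2.2 say repeatedly that the model is fixed, and section 2.2 assigns the locked baseline score to the primary analyses. Section 2.1 lists two uses without saying that the refined predictions are the ones compared with events. Section 6.1 calls the analyses mainly exploratory. Much of this stands: an AUC from the locked baseline score is a proper validation, and later refinement does not undo it. What does not stand is that the text is therefore consistent. An exploratory label does not reconcile a fixed model with a refined one, and two incompatible uses of the same data are a matter of what the protocol states, not detail left to an analysis plan.

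Three stronger readings are tempting and are not supported.

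- **That the study is not a validation at all.** This does not follow, because section 2.2 provides for the locked-score comparison.
- **That the Practical use instruction, "Fit a multivariable Cox model with one or more of the following predictors-X", refits the model in this cohort.** It names no cohort. It refers to five ApoE genotype categories, whereas carriers of at least one ε4 allele can have only three genotypes (ε2/ε4, ε3/ε4, ε4/ε4). Section 2.2 places Cox model fitting in the source cohorts.
- **That the Cox analyses in section 6.1, "as a function of baseline P&R risk, PRS, ApoE4 dose, and biomarker levels", undo the validation.** Entering a fixed score as a covariate does not re-estimate it or change its AUC. The wording also allows separate models.

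**Conclusion.** The concern holds as an unresolved contradiction about the role of the study data. Section 2.1 allows refinement on the cohort that aim 1 and section 2.2 reserve for validating a fixed model, and section 6.1 does not identify the version behind the reported AUC. It bears on primary aim 1 and should be settled before outcomes accrue.

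The size is conditional. If the reported AUC came from a full refit in this cohort, a model with no discrimination would show a mean AUC of about 0.65–0.79 (5 predictors) or 0.72–0.91 (11 predictors). That rests on assumed conversion of 5–20%, N of 90–100, independent predictors and no optimism correction; the protocol gives neither an event rate nor the number of quantities to be refined. If the locked baseline score is used, there is no such bias.

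The PRS reference is a lesser inconsistency with the claim that the model comes only from existing data. It uses no outcomes and appears only as an example. Its consequence lies in calibration and category assignment, not in the AUC.

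**What to change.** - **Section 2.1:** delete *and refine*, or state that any refinement is a separate exploratory step, done after the locked-score result is reported, labelled as model updating and presented with optimism correction.
- **Section 6.1:** state that the primary AUC and calibration use only the locked baseline score.
- **PRS section:** delete *plus early enrollees*, and fix the PRS mean, SD and cut-offs from external data.
- **Section 2.2:** state that the lock, including the PRS scaling, precedes the first baseline score.
- **Practical use (clarification only):** name the dataset in which that Cox model is fitted.

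The cost is protocol wording; no visit, sample or participant is added. The reported AUC may be less favourable than one from a refined model.
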